#### **6.1.3.1 Sensitivity analyses**

Subjects are able to take a rescue medication at least 30 minutes following study medication administration. As a sensitivity analysis, the logistic regression analysis shall be repeated on all timepoints, where only the timepoints with at least 50% of non-missing data will be kept.

The logistic regression analysis with baseline headache severity (very severe, severe or moderate), CH type (episodic or chronic), dose (0 for placebo, 1.5 mg or 0.9 mg for SOM230), time and dose by time interaction as fixed effects and subject as a random effect will be used to assess the effect of SOM230 on headache response. Dose and time will be included as categorical variables in the model. Placebo adjusted headache response rate at each time point will be provided. Headache response measurements after 100% oxygen therapy or sumatriptan will be set to missing, which will be considered as missing at random. The frequency and percentage of subjects with each response shall be displayed, along with the mean estimates, 90% confidence interval and p-value from the logistic regression analysis.

The sensitivity logistic regression will only be performed if the primary analysis indicates a significant result.

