Subjects will be required to complete a patient diary to document the pain severity and pain relief before and after the administration of the study medication. In case the pain is not responding to the administered study drug after 30 minutes, subjects will be allowed to use only 100% oxygen or sumatriptan as a rescue management. If applicable and feasible, subjects in Period 1 may return to the study center for follow-up within 24 hour post treatment administration. The subjects will have a follow-up within 24 hours of the study drug administration in Period 2 where a PK sample will be collected, with a second PK sample collected to 1 to 2 hours after the 1st PK sample. In case the follow-up visit in Period 2 falls on a weekend, a window of up to 48 hours may be considered.

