#### **6.1.2 Descriptive analyses**

If the second cohort (0.9 mg dose) is assessed then cohort will serve as a grouping factor for all relevant data listings.

The headache response will be defined at each post-dose timepoint separately and will be summarized by cohort, treatment and visit/timepoint using frequency tables. Percentage of subjects having received 100% oxygen therapy or sumatriptan at each time point will be tabulated by cohort and treatment.

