#### **6.1.3.2 Handling of missing values/censoring/discontinuations**

Assuming missing at random, a subject with missing value at a time point will still contribute to the estimation of the treatment effect at that particular time point as the likelihood-based repeated measures analysis borrows information from non-missing values of this subject and other subjects.

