#### **6.1.3.3 Graphical presentation of results**

If there are sufficient data to analyze, then the time to headache response, time to pain free response and time to recurrence curves, using Kaplan-Meier estimates will be constructed by dose. A clustered log-rank test for correlated survival data will be performed to compare the time to event curves between treatments while hazard ratios will be estimated by the Cox proportional hazard frailty model with CH type and baseline headache severity or frequency included as covariates as appropriate. If subjects do not have an event, they will be censored at their last available visit. These analyses will only be conducted if the primary analysis indicates a significant result and if there is sufficient data.

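### After 30 minutes, setting post-rescue measurements to missing makes later response frequencies understate the drug-placebo difference, and the mixed model corrects this only if responses within an attack are no more alike than the subject effect allows

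*SAP*

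**What the plan says.** **When rescue is allowed.** SAP 1.4 gives the condition: "In case the pain is not responding to the administered study drug after 30 minutes". SAP 6.1.3.1 gives the earliest time: "Subjects are able to take a rescue medication at least 30 minutes following study medication administration".

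**What happens to later data.** SAP 6.1.3.1: "Headache response measurements after 100% oxygen therapy or sumatriptan will be set to missing, which will be considered as missing at random". SAP 6.2.1.3 applies the same rule to pain-free data. The over-time analysis repeats the logistic regression on all time points, "where only the timepoints with at least 50% of non-missing data will be kept", with "time and dose by time interaction as fixed effects and subject as a random effect". It also displays response frequencies and percentages. It runs only if the primary analysis is significant.

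**Justification.** SAP 6.1.3.2 relies on the repeated-measures likelihood: "a subject with missing value at a time point will still contribute to the estimation of the treatment effect at that particular time point".

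**Tables and curves.** SAP 6.1.2: "The headache response will be defined at each post-dose timepoint separately". Those tables are not conditional on the primary result, and the section gives neither a rescue rule nor a denominator. SAP 6.1.3.3 plans time-to-response curves, also conditional on a significant primary result. It does not mention rescue, and its censoring rule is "If subjects do not have an event, they will be censored at their last available visit".

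**Protocol.** Section 11.4.2 has the same set-to-missing rule for oxygen. Section 11.4.4 adds a supportive model with oxygen as a time-dependent covariate, so that post-oxygen data are kept. SAP 1.1 says that the SAP implements the protocol's analysis, but SAP 6.1.3 and 6.1.4 do not contain that model.

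**The concern.** Failure to respond is what permits rescue, and rescue is what removes the later values. At the planning rates, failures are more common under placebo (70%) than under SOM230 (28%), so deletion falls mainly on placebo. A percentage of the values that remain is then too high in both treatments, and more so for placebo.

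The likelihood argument in SAP 6.1.3.2 applies to the model, not to displayed frequencies. In the model, the only random effect is the subject, shared by the placebo attack and the drug attack. A 30-minute failure therefore informs later times in its own attack no more strongly than it informs the other attack. Pain within one attack is plausibly more alike than that.

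At stake is the description of effect after 30 minutes in a study meant to decide on further development. The error would tend to understate a working drug.

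**Working it through.** **The plan's own figures.** The documents give no figure for any time after 30 minutes. The nearest is about 80% power at 30 minutes with 23 subjects per cohort (protocol 11.6). Exact enumeration of paired outcomes with the stated inputs gives 88.2% (normal approximation 85.0%). The simulation behind the stated figure is not described; requiring a net gain of 8 of 23 instead of 7 gives 79.2%. Nothing below depends on power.

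**Inputs from protocol 11.6.** Response at 30 minutes of 30% on placebo and 72% on SOM230; correlation 0.25; 23 evaluable subjects.

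**Assumed inputs.** Share *r* of non-responders taking rescue; diary times 15, 30, 45 and 60 minutes; later response rates; extra correlation within an attack.

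**Step 1: frequencies just after 30 minutes.** Suppose responders stay responders, unrescued non-responders stay non-responders, and percentages are taken over non-missing values. With response rate *p*:

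- non-missing share = p + (1 − p)(1 − r)
- displayed rate = p / [p + (1 − p)(1 − r)]

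For r = 75%: placebo 0.30 / (0.30 + 0.70 × 0.25) = 0.30/0.475 = 63%; SOM230 0.72 / (0.72 + 0.28 × 0.25) = 0.72/0.79 = 91%.

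| r | Non-missing: placebo / drug / pooled | Displayed: placebo vs drug | Difference (true 42) |
|---|---|---|---|
| 50% | 65% / 86% / 75.5% | 46% vs 84% | 38 |
| 75% | 47.5% / 79% / 63% | 63% vs 91% | 28 |
| 90% | 37% / 75% / 56% | 81% vs 96% | 15 |
| 100% | 30% / 72% / 51% | 100% vs 100% | 0 |

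**Step 2: the SAP's mixed model.** This is a large-sample simulation (40,000 subjects, two attacks each). The random-subject logistic model was fitted by maximum likelihood to all time points, before any 50% rule. Assumed true rates are 35% vs 75% at 45 minutes and 40% vs 78% at 60 minutes. The true differences are 40 to 41 and 38 points. The subject SD is 1.2, with extra runs at 0.8 for attack SD 4. Entries are differences in points.

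| Attack-level SD | Rescue per step | 45 min: frequency / model / rescue as non-response | 60 min: frequency / model / rescue as non-response |
|---|---|---|---|
| about 0 | 50% | 40 / 41 / 42 | 35 / 38 / 41 |
| about 0 | 90% | 34 / 40 / 43 | 25 / 38 / 40 |
| 2 | 50% | 37 / 39 / 41 | 30 / 35 / 41 |
| 2 | 90% | 27 / 34 / 42 | 13 / 26 / 41 |
| 4 | 50% | 37 / 38–39 / 41 | 27–28 / 32–33 / 41 |
| 4 | 90% | 21 / 28–29 / 42 | 7–8 / 17–18 / 41 |

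At 30 minutes there is no bias in any run. With no extra within-attack correlation the model recovers the no-rescue difference, although the frequencies still shrink. With extra correlation the model moves towards zero. The between-attack correlation in these runs is 0.01 to 0.17, below the protocol's 0.25, so the biased rows are illustrations and not predictions.

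**Step 3: the 50% rule.** With 23 subjects at the planning rates and correlation 0.25, at the first time point after rescue:

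| r | Kept, pooled reading | Kept (pooled) with under half of placebo data | Kept, per-treatment reading |
|---|---|---|---|
| 75% | 98% | 57% | 40% |
| 90% | 83% | 73% | 10% |

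Which times are reported therefore depends on the data and on a reading that the SAP does not state.

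The rule also limits the harm. In step 2 with 90% rescue, pooled non-missing data at 60 minutes are 40% to 47%. Even a pooled rule would usually drop the time point with the largest model bias.

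**The case against.** The strongest case against is that little rests on these outputs. Headache response and pain-free response are both defined at 30 minutes, the primary model uses 30-minute data only, and rescue starts no earlier. The over-time model and the curves follow only a significant primary result, in a study that calls itself non-confirmatory. All of this stands and sets the priority.

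A reader might infer that the model uses only subjects who needed no rescue. The documents do not support that. Rescued subjects' earlier values and their other attack stay in the likelihood (SAP 6.1.3.2). If rescue depends only on recorded pain, missing at random can hold, and step 2 shows no bias when the model is right. What remains is a conditional weakness, the missing attack-level effect.

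A reader might also blame the 50% rule for the bias. It removes the most depleted time points; its defects are that it depends on the data and is undefined as to pooling.

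The tables in SAP 6.1.2 state no denominator. With all treated attacks as denominator, the step 1 data would show 30% vs 72%, so the shrinkage there assumes percentages of non-missing values. In SAP 6.1.3.1 the frequencies follow directly on the set-to-missing rule, which makes that the natural reading.

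The curves could be read as crediting relief after oxygen to study drug. SAP 6.1.3.3 is silent, and carrying over the set-to-missing rule is at least as natural. Its censoring term need not mean a clinic visit, since SAP 6.1.2 speaks of visits and time points together. Only the silence is a defect.

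Finally, the SAP does plan tables of rescue use, a conditional Cox model for time to rescue and an optional joint model (SAP 6.1.2, 6.2.1.2, 6.1.4). These describe rescue; apart from the optional joint model, none corrects the later response rates.

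**Conclusion.** The concern holds in a limited form, with optional to minor priority. Later response frequencies over non-missing values understate the difference: 38, 28 or 15 points instead of 42 for rescue fractions of 50%, 75% or 90%, if responses persist. The model is unbiased without extra within-attack correlation. With it, the model gives 28 to 39 points at 45 minutes (true 40 to 41) and 17 to 35 at 60 minutes (true 38). The low end at 60 minutes falls where the 50% rule would usually drop the time point. All sizes after 30 minutes rest on assumed later rates, diary times, rescue fractions and attack-level SDs.

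Three gaps need no assumption: the 50% rule does not say pooled or per treatment, SAP 6.1.3.3 does not say how rescue is handled, and the protocol's supportive analysis keeping post-oxygen data is absent from SAP 6.1.3 and 6.1.4. It would be wrong to conclude that the 30-minute primary or pain-free result is distorted.

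**What to change.** 1. In SAP 6.1.2, 6.1.3.1 and 6.2.1.3, for times after 30 minutes, report response and pain-free rates with measurements after rescue counted as non-response. Put all treated attacks in the denominator and keep all diary time points; this analysis then needs no 50% rule. State that it stands in place of the protocol 11.4.4 model with oxygen as covariate, or restore that model.
2. Keep the set-to-missing mixed model as secondary, with an attack-level (subject-by-period) random effect if it can be estimated, and apply the 50% rule per treatment.
3. In SAP 6.1.3.3, treat rescue before response as non-response held to the end of the diary window.
4. Reconcile the rescue definition: SAP 1.4 names oxygen or sumatriptan, while protocol 3.1 and 6.9 name oxygen only. The definition decides which measurements are affected.

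**Cost.** SAP wording and simple recoding, with no new data. The later-time estimate becomes response without rescue, not response had rescue been unavailable. In step 2 these differ by about 2 to 3 points at 60 minutes (40 to 41 against 38). With 23 subjects the attack-level effect may not be estimable, which is why it is conditional and secondary.

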### **11.4.2 Statistical model, hypothesis, and method of analysis**

A logistic regression analysis with baseline headache severity, CH type, dose, and dose by time interaction as fixed effects and subject as a random effect will be used to assess the effect of SOM230 on headache response over time. Dose and time will be included as categorical variables in the model. Placebo adjusted headache response rate at each time point will be provided. Headache response measurements after 100% oxygen therapy will be set to missing, which will be considered as missing at random.

The following approaches will be taken if the 0.9 mg dose is assessed in the second cohort:

Placebo adjusted headache response rate at each time point will be obtained for each of the two SOM230 doses. A linear dose-response trend test will be constructed within the logistic regression framework using a contrast with the first order orthogonal polynomial coefficients. Pairwise comparisons and further dose-response assessments will be performed as appropriate. If there is no difference between the two SOM230 doses then a comparison between the pooled SOM230 treatment and placebo will be conducted.

A subgroup analysis for non-sumatriptan users may be conducted as needed.

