#### **6.1.3 Statistical model, assumptions and hypotheses**

A logistic regression analysis on the 30 minutes post-dosing data only with baseline headache severity (very severe, severe or moderate), CH type (episodic or chronic) and dose (0 for placebo, 1.5 mg or 0.9 mg for SOM230) as fixed effects will be used to assess the effect of SOM230 on headache response. Dose will be included as a categorical variable in the model. Placebo adjusted headache response rate will be provided. Headache response measurements after 100% oxygen therapy or sumatriptan will be set to missing, which will be considered as missing at random. The frequency and percentage of subjects with each response shall be displayed, along with the mean estimates, 90% confidence interval and p-value from the logistic regression analysis.

The following approaches will be taken if the 0.9 mg dose is assessed in the second cohort:

Placebo adjusted headache response rate will be obtained for each of the two SOM230 doses. A linear dose-response trend test will be constructed within the logistic regression framework using a contrast with the first order orthogonal polynomial coefficients. Pairwise comparisons and further dose-response assessments will be performed as appropriate. If there is no difference between the two SOM230 doses then a comparison between the pooled SOM230 treatment and placebo will be conducted.

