#### **6.1.4 Supportive analyses**

The McNemar test with or without stratification by CH type may also be used to compare headache response rates between treatments at 30 minutes post-dosing only.

If there are sufficient data to analyze, a Cox proportional hazard model with dose and CH type as classification factors and headache severity as a time dependent covariate will be used to analyze time to 100% oxygen therapy or sumatriptan. A random subject effect will be included in the model as well to account for the correlation among measurements from the same subject. This model will only be performed if the primary analysis indicates a significant result and there is sufficient data.

Joint modelling of the headache response and time to 100% oxygen therapy or sumatriptan data may be attempted as appropriate. This analysis will only be performed if a good response rate at 30 minutes versus placebo is detected.

Finally to avoid reducing statistical efficiency due to analyzing the dichotomized data, the headache severity measurements over time may be analyzed using a proportional-odds model similar to the aforementioned logistic regression model.

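### The SAP runs its over-time and time-to-event comparisons only after a significant 30-minute result, a condition absent from the protocol's over-time and time-to-oxygen models

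*SAP*

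**What the plan says.** The SAP's primary analysis is "A logistic regression analysis on the 30 minutes post-dosing data only" (6.1.3), reported "along with the mean estimates, 90% confidence interval and p-value from the logistic regression analysis". Three blocks depend on its outcome:

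- **Response over time.** The repeated-measures logistic model with a random subject effect (6.1.3.1): "The sensitivity logistic regression will only be performed if the primary analysis indicates a significant result".
- **Time to response, time to pain free and time to recurrence.** Kaplan-Meier curves, clustered log-rank test and Cox frailty model (6.1.3.3): "These analyses will only be conducted if the primary analysis indicates a significant result and if there is sufficient data".
- **Time to rescue.** The Cox model (6.1.4): "This model will only be performed if the primary analysis indicates a significant result and there is sufficient data".

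The joint model of response and rescue has a different trigger, also undefined: "This analysis will only be performed if a good response rate at 30 minutes versus placebo is detected".

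In the protocol, the over-time logistic model belongs to the primary analysis itself. Section 11.4.2 says that it "will be used to assess the effect of SOM230 on headache response over time". Section 11.4.4 plans the Cox model of time to oxygen therapy. Neither carries a significance condition.

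Some outputs in the SAP are unconditional. Section 6.1.2 says: "The headache response will be defined at each post-dose timepoint separately and will be summarized by cohort, treatment and visit/timepoint using frequency tables". It also tabulates rescue use at each time point. Section 6.2.1.2 tabulates pain-free status and autonomic symptoms over time. Section 6.1.4 leaves the proportional-odds model of severity over time optional but without a significance condition.

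**The concern.** A sensitivity analysis should show whether the primary conclusion, positive or negative, survives a different analysis. One that runs only after a positive result can never question a negative one.

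The SAP says that it implements the protocol's planned analysis, but it adds this condition without giving a reason. The study calls itself non-confirmatory, so the condition is not needed for error control.

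Three features of this trial make it matter:

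- **The purpose is a development decision.** Protocol 1.2 asks whether efficacy and safety warrant further work. A modest or later effect bears on that decision.
- **The next attack is part of the rationale.** Protocol 3.2 expects a single dose to delay the next attack. Such a delay need not follow 30-minute relief, yet the recurrence analysis is dropped when the 30-minute test fails.
- **The trigger is undefined.** The visible SAP gives no level or sidedness and, if both doses are studied, does not say which comparison counts. That leaves the decision to be made after the result is known.

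In addition, SAP 6.1.3.2 relies on a repeated-measures likelihood to handle missing values. The primary model uses one time point and has no subject effect. The only planned response models that fit that description are the conditional one and the optional proportional-odds model.

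**Working it through.** **1. Inputs.** Protocol 11.6 gives 23 subjects per cohort, response rates of 30% (placebo) and 72% (SOM230), and correlation 0.25. Protocol 1.1 cites 36% vs 52% from the octreotide trial. The 30% vs 60% case and the case with no difference (30% vs 30%) are assumptions.

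**2. Paired cell probabilities.** With placebo rate p0, active rate p1 and correlation r:

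- both respond: p11 = p0·p1 + r·√[p0(1−p0)·p1(1−p1)]
- active only: p1 − p11; placebo only: p0 − p11

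At 30% vs 72%, p11 = 0.216 + 0.25 × √(0.21 × 0.2016) = 0.267. Active only is then 0.453 and placebo only is 0.033.

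**3. The protocol's own figure.** Section 11.6 states about 80% power for an estimated difference of at least 30% together with at least 90% probability of a positive effect. Exact enumeration over 23 pairs gives 88.2% if the raw difference must reach 7/23 (30.4%). It gives 79.2% if 8/23 is needed, which is what a posterior-mean difference under a Beta(1,1) prior requires: (difference in responders)/25 ≥ 0.30 means at least 7.5, so 8. The stated figure is reproduced on that second reading.

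**4. What significant could mean.** The SAP's 90% interval excluding no effect, in favour of SOM230, corresponds to one-sided 0.05. The 90% probability in protocol 11.6 corresponds to about one-sided 0.10. Both levels were used, each with two tests. Let b and c be the numbers responding only on active and only on placebo, and x1 and x0 the responders on active and placebo, with n = 23:

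- paired Wald: z = (b − c)/√[b + c − (b − c)²/n]
- unpaired logistic Wald without covariates: z = log odds ratio/√[1/x1 + 1/(n−x1) + 1/x0 + 1/(n−x0)], adding 0.5 to each cell when one is empty

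**5. Probability that the condition fails and the analyses are not run** (exact enumeration, no missing data):

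| True rates at 30 min | Paired, 0.10 | Paired, 0.05 | Unpaired, 0.10 | Unpaired, 0.05 |
|---|---|---|---|---|
| 30% vs 72% | 1.0% | 2.7% | 2.7% | 6.0% |
| 30% vs 60% | 11.0% | 19.9% | 19.2% | 30.5% |
| 36% vs 52% | 47.4% | 61.7% | 60.8% | 73.5% |
| 30% vs 30% | 88.4% | 93.5% | 93.4% | 97.3% |

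The spread along a row shows how far the undefined term alone can move the outcome.

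**6. Outputs after a non-significant 30-minute result.**

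| Question | Still produced | Not produced |
|---|---|---|
| Response over time | Frequency tables; optional proportional-odds model | Adjusted response differences with 90% intervals |
| Time to response, pain free, recurrence | Pain-free tables over time | Curves, log-rank test, hazard ratios |
| Time to rescue | Rescue percentages by time point | Cox model |

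**The case against.** The strongest reply is that little is really hidden. Response, rescue and pain-free status by time point are tabulated whatever happens, and the proportional-odds model stays available. The endpoint is fixed at 30 minutes, and protocol 1.1 describes attacks of 15 to 60 minutes. Rescue is allowed after 30 minutes and later values are then set to missing, so the conditional models may have thin data. The conditions are also written down in advance. At the design effect they hardly ever bite.

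Much of this stands. A reader might infer that a late effect would never be examined. The documents do not support that, because the unconditional tables would show it. What is lost is the formal comparison. Crude tables are a weak substitute once rescue has begun, but they exist.

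A reader might also infer that the condition inflates the later estimates in a positive trial. That does not follow. The 30-minute estimate is reported in every trial. Once a trial is positive, its later estimates are the same numbers with or without the condition, so removing it would not change them.

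Nor can a departure from the protocol be shown for the time-to-response block. It has no visible protocol counterpart, and protocol 11.5.1 is partly redacted.

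The reply does not explain why two models that the protocol plans unconditionally became conditional. Thin data are already covered by the SAP's separate data-sufficiency wording.

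**Conclusion.** The point holds in a limited form. Three blocks of analysis depend on an undefined significant result at 30 minutes. For the over-time model and the time-to-oxygen model, this departs from the protocol. After a non-significant result, the trial keeps descriptive tables and one optional model, and loses the adjusted estimates, curves and hazard ratios.

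The size depends on the true effect. The condition fails in about 1 to 6% of trials at the planned 42-point effect, 11 to 30% at 30 points, 47 to 74% at the 16 points cited for octreotide, and 88 to 97% with no difference at 30 minutes. In the last case the loss matters only if there is a later effect or a delay in recurrence. These figures assume 23 complete pairs, correlation 0.25, no covariates, and one-sided levels of 0.05 to 0.10. The documents do not fix the test level for this purpose.

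This should be corrected before database lock. It does not affect the primary 30-minute estimate, the sample size or the power.

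**What to change.** In SAP 6.1.3.1, 6.1.3.3 and 6.1.4, delete the clauses that make these analyses depend on a significant primary result. Keep the data-sufficiency condition as the only one, and apply it to models that cannot be fitted. State that the analyses are run and reported whatever the 30-minute result, and label them supportive or exploratory.

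The cost is a change of SAP wording and, after a negative primary result, a few more tables and figures. Some of these may rest on sparse data after rescue, which the report should say. No new data and no further patients are needed.
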